- FEV1< 60% predicted with more than mild abnormalities on lung imaging
- Requirement of > 1 diuretic adjustment in the prior 30 days
- Preferred form of activity is not measured by an activity tracker (swimming, ice skating, stair master, or activities on wheels such as bicycling or rollerblading)
- Type I diabetes mellitus
- Prior diagnosis of cirrhosis
- Untreated hypo- or hyper-thyroidism
- eGFR by MDRD <40mL/min

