1.16 Metformin or Placebo

Subjects will receive metformin 500mg or equivalent placebo tablets via overnight shipment in adequate time for week 1. Patients will titrate the medication as follows: 1 Every Day x 5 days, 1 BID x 5 days, 1 TID x 5 days, and then 2 BID for the duration of the trial. This titration schedule is based on the excellent tolerability from our pilot study. Patients in the placebo group will have matching sugar pills prepared by the research pharmacy at Vanderbilt University Medical Center. Medication should be taken by participants all the way up to their Visit #2 date.

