1.22.8 Blood Biomarkers

a. HOMA-IR

Insulin resistance will be quantified using the homeostatic model assessment of insulin resistance (HOMA-IR), which estimates insulin resistance through fasting plasma insulin and glucose ratios, at screening and 12 weeks.

b. Lipid Metabolism

Altered lipid metabolism reflects insulin resistance. Fasting plasma lipid metabolites will be evaluated via non-targeted metabolomics screen. Mass spectroscopy of approximately 300 metabolites across all major metabolic pathways will be performed at screening and 12 weeks.

c. Fatty Acid Metabolism

Elevated circulating fatty acids and acylcarnitines contribute to RV lipotoxicity and indicate insulin resistance associated with pulmonary hypertension. To evaluate the effect of this intervention on fatty acid metabolism, we will measure fasting long-chain fatty acid and acylcarnitine profiles using mass spectrometry at screening and 12 weeks.

d. Plasma and Urine Estradiol and Estrogen Metabolites

Estrogen metabolites are associated with pulmonary hypertension in human PAH subjects. Estrogen metabolism we will be evaluated by measuring plasma estradiol (E2) and estrogen metabolites, including 2ME and 16 α OHE, using mass spectrometry at screening and 12 weeks.

e. Plasma NT-proBNP

Plasma NT-proBNP reflects right ventricular function in PAH and is a strong predictor of outcome in PAH. BNP will be assessed at screening and 12 weeks.

f. Amino Acids and Metabolomics

We and others have observed in cross-sectional studies that PAH is associated with insulin resistance and lipid abnormalities. Metabolites associated with insulin resistance and lipid metabolism have not been examined in the context of a clinical trial targeting insulin resistance. Changes in amino acids and metabolomic profiles with metformin and physical activity may provide insight into the mechanisms by which these interventions may improve insulin resistance (and outcomes) in patients with PAH.

g. Safety Labs

A comprehensive panel, complete blood count, hemoglobin A1c, and a urine pregnancy test will be assessed at screening and 12 weeks.

1.22.9 *Transthoracic Echocardiographic Measures*

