1.33 Metformin

This drug has been on the market for several decades and is considered first line therapy for diabetes mellitus type 2. Moreover, it has been used extensively in non-hyperglycemic patients with polycystic ovarian disease. Additional studies of the safety of metformin in heart failure have been published. The pertinent risk of metformin is development of lactic acidosis. This risk has been reported primarily in patients with abnormal renal or hepatic function, thus we have chosen to exclude these populations from the study. Additional concerns include hypoglycemia, though this is a rare risk of this drug, and gastrointestinal distress. Patients will be educated on the signs and symptoms of hypoglycemia and advised to contact study staff immediately if any arise. Several other potential side effects listed in the package insert that will be monitored at

study visits and through phone conversation if need arises. We will monitor patients at baseline, week 1, week 3, week 6, week 9, week 12, week 15, and week 17 through either a visit or phone conversation. At these points, side effects that limit dose adjustment will be assessed. If patients report significant gastrointestinal effects, metformin will not be increased as would otherwise occur in the protocol. If symptoms persist further, the dose will be dropped by 500 mg daily to the highest tolerated dose.

The most common adverse reactions experienced are:

- >10% of patients: diarrhea (instant release tablet: 12% to 53%; extended release tablet: 10% to 17%), nausea/vomiting (instant release tablet: 7% to 26%; extended release tablet: 7% to 9%), flatulence (12%), Weakness (9%)
- 1% to 10%: chest discomfort, flushing, palpitation, headache (6%), chills, dizziness, lightheadedness, rash, hypoglycemia, Indigestion (7%), abdominal discomfort (6%), abdominal distention, abnormal stools, constipation, dyspepsia/heartburn, taste disorder, myalgia, dyspnea, upper respiratory tract infection, decreased vitamin B₁₂ levels (7%), increased diaphoresis, flu-like syndrome, nail disorder
- <1% (Limited to important or life-threatening): lactic acidosis, leukocytoclastic vasculitis, megaloblastic anemia, pneumonitis

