- Contraindications to the use of metformin are: hypersensitivity to metformin or any component of the formulation; renal disease or renal dysfunction (serum creatinine ≥ 1.5 mg/dL in males or ≥ 1.4 mg/dL in females) or abnormal creatinine clearance from any cause, including shock, acute myocardial infarction, or septicemia; acute or chronic metabolic acidosis with or without coma (including diabetic ketoacidosis)

1.33.1 *Boxed Warning*

A boxed warning has been issued for metformin related to the risk of developing lactic acidosis. The risk is increased in patients with acute congestive heart failure, dehydration, excessive alcohol intake, hepatic or renal impairment, or sepsis. Conditions that increase the risk of lactic acidosis on metformin treatment are all exclusion criteria for this study. Based on our pilot trial with no lactic acidosis in enrollees thus far, we do not anticipate this to be a significant complication. If clinically significant lactic acidosis is diagnosed for clinical indications, the DSMB and IRB will be notified as per protocol.

1.33.2 *Iodinated Contrast*

Metformin therapy will be discontinued prior to or at the time of intravascular administration of iodinated contrast media (potential for acute alteration in renal function) should a subject require contrast during the course of this study. Metformin will be withheld for 48 hours after the radiologic study and restarted only after renal function has been confirmed as normal. Patients will be encouraged to delay any elective radiologic studies requiring iodinated contrast until the conclusion of the study.

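### Section 1.33.1 says every condition that raises lactic acidosis risk is an exclusion criterion; three of the six it names have no entry in 1.9, and the eGFR 40 limit admits subjects who meet the creatinine contraindication in 1.33

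*Combined protocol and SAP*

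**What the plan says.** Section 1.33 (Metformin) names lactic acidosis as the pertinent risk, says it is reported mainly with abnormal renal or hepatic function, and continues: "thus we have chosen to exclude these populations from the study". Its contraindication bullet includes "renal disease or renal dysfunction (serum creatinine ≥ 1.5 mg/dL in males or ≥ 1.4 mg/dL in females", followed by abnormal creatinine clearance from any cause.

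Section 1.33.1 (Boxed Warning) lists the risk conditions: "The risk is increased in patients with acute congestive heart failure, dehydration, excessive alcohol intake, hepatic or renal impairment, or sepsis". It then says: "Conditions that increase the risk of lactic acidosis on metformin treatment are all exclusion criteria for this study". It closes by citing the pilot study, with no lactic acidosis so far, as the reason for not expecting a significant complication.

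The exclusion list in 1.9 (Inclusion/Exclusion Criteria), repeated in the Protocol Summary, has one renal entry, "eGFR by MDRD <40mL/min", and one hepatic entry, "Prior diagnosis of cirrhosis".

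Section 1.16 takes the 500 mg tablets up in three five-day steps, "and then 2 BID for the duration of the trial". On laboratory safety, 1.22.8 says: "A comprehensive panel, complete blood count, hemoglobin A1c, and a urine pregnancy test will be assessed at screening and 12 weeks".

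**The concern.** Someone who reads only the risk section, such as an IRB or DSMB member, is told that entry criteria remove everyone at raised risk of lactic acidosis. If the list does not do that, the plan claims a protection it lacks. Half of those randomised (80 of 160) are assigned metformin, rising to 2,000 mg a day with no limit tied to renal function.

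Some of the uncovered states are foreseeable here. Subjects may be on diuretics. Section 1.33 quotes diarrhea in 12% to 53% of patients on instant-release tablets, and 1.6 reports mild diarrhea in all pilot patients. Dehydration during treatment is therefore a practical question. Section 1.33.2 gives a hold rule for iodinated contrast, but no rule is given for dehydration, sepsis or acute heart failure.

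**Working it through.** **Check 1: the six conditions in 1.33.1 against the list in 1.9.** This uses the documents alone.

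| Condition in 1.33.1 | Entry in 1.9 | Covered? |
|---|---|---|
| Acute congestive heart failure | WHO class IV; more than one diuretic adjustment in 30 days | In part |
| Dehydration | None | No |
| Excessive alcohol intake | None | No |
| Hepatic impairment | Prior cirrhosis only | In part |
| Renal impairment | MDRD eGFR below 40 | In part (check 2) |
| Sepsis | None | No |

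Two entries might be read as catch-alls. The exclusion for active drug use applies only to drug- and toxin-associated PAH and does not mention alcohol. The exclusion for other activity-limiting conditions concerns the ability to be active and names none of the three. So 3 of 6 have no entry.

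**Check 2: does eGFR 40 enforce the creatinine contraindication?** The protocol names MDRD but does not print it. Assumed form:

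eGFR = k × Cr^(−1.154) × age^(−0.203) × 0.742 if female, with k = 175 or 186 and no race term.

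Man, Cr 1.5, age 50, k = 175: 175 × 0.626 × 0.452 = 49.5, above 40, so eligible.

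| At the 1.33 limit | k | Age 18 | 30 | 50 | 70 | 90 |
|---|---|---|---|---|---|---|
| Man, Cr 1.5 | 175 | 61.0 | 55.0 | 49.5 | 46.3 | 44.0 |
| Man, Cr 1.5 | 186 | 64.8 | 58.4 | 52.7 | 49.2 | 46.7 |
| Woman, Cr 1.4 | 175 | 49.0 | 44.2 | 39.8 | 37.2 | 35.3 |
| Woman, Cr 1.4 | 186 | 52.1 | 46.9 | 42.3 | 39.5 | 37.5 |

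Men at the limit pass at every adult age. For women the crossing age is (k × 0.742 × 1.4^(−1.154) / 40)^(1/0.203), which is 48.8 years for k = 175 and 65.9 for k = 186. Women at 1.4 are therefore admitted to about 48 or 65 and excluded beyond that. If a race factor (1.212 or 1.210) is applied, both sexes at the limit pass through age 90; the lowest value is 42.8.

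Solving for the creatinine at which a man reaches eGFR 40, Cr = (k × age^(−0.203) / 40)^(1/1.154):

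- Age 50: 1.81 (k = 175) or 1.90 (k = 186) mg/dL.
- Age 70: 1.70 or 1.79 mg/dL.

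So an eligible 50-year-old man may have a creatinine from 1.5 to about 1.8 or 1.9, all within the contraindicated range.

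**Exposure.** Titration takes 5 + 5 + 5 = 15 days, then 2 × 500 mg twice daily = 2,000 mg/day. Drug is taken up to Visit 2, scheduled in Table 2 at day 84 ± 5, so time at full dose is at most 89 − 15 = 74 days. Screening is 14 to 30 days before day 0, so scheduled panels are 79 + 14 = 93 to 89 + 30 = 119 days apart.

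**The case against.** **Sepsis and dehydration are not enrolment categories.** They are acute states, and an ambulatory subject on a three-month stable regimen is unlikely to have either at entry. No entry criterion can prevent sepsis in week 6. This stands, and it argues for a hold rule over new exclusions. Excessive alcohol intake is the one plain omission from the list. None of this makes the word all correct.

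**The low-concern conclusion cites the pilot.** That is so, and 1.6 describes the same maximum dose. But the pilot had 16 patients. With no events in 16, the one-sided 95% upper bound is 1 − 0.05^(1/16) = 0.17, which cannot stand in for exclusions that were not made.

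**The creatinine figures are label-style text in a risk section.** Randomisation depends on 1.9 alone, and the revision history shows the eGFR limit was revised in versions 3.1 and 6. Quite possibly eGFR 40 was chosen deliberately and the risk text was not aligned with it. That would explain the conflict, but the two current sections still disagree.

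**Other safeguards exist.** There are safety contacts at weeks 1, 3, 6 and 9, dose reduction for persistent gastrointestinal symptoms, laboratory tests when clinically indicated, DSMB review about every four months, and withdrawal for safety. These limit harm, but they are not the exclusions that 1.33.1 describes.

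A reader might infer that two sites would treat the same subject differently, one following 1.9 and the other 1.33. The documents do not support this: only 1.9 governs entry, an investigator confirms it, and the coordinating center issues common procedures. A reader might also infer that eGFR 40 is itself unsafe. The documents show only that it does not match the contraindication printed in 1.33.

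**Conclusion.** Wrong as written. The finding that three of the six conditions have no exclusion, and that two non-renal ones are covered only in part, is exact and needs no assumption. The renal finding rests on the assumed MDRD form. For men it holds under both constants, with or without a race term. For women without a race term it is confined to younger ages.

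The number of subjects affected cannot be derived, because the documents give no creatinine distribution; any count would be a guess. It would also be tempting to read this as a threat to the efficacy result. Nothing in the documents supports that, and no effect on the primary endpoint is claimed. The defect is a safety property stated in the plan that the eligibility list does not deliver.

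**What to change.** - Replace the sentence in 1.33.1 with a statement of what 1.9 actually excludes, and align the similar claim in 1.33.
- Use one renal limit in both sections. Either keep eGFR 40, give the reason and remove the creatinine figures from 1.33, or add creatinine of at least 1.5 mg/dL (men) and 1.4 mg/dL (women) to the exclusions in 1.9.
- Add excessive alcohol intake to 1.9 if enrolment is still open. The documents do not say whether it is; if closed, this item affects nobody.
- State in 1.33.1 that study drug (metformin or placebo, so the blind is kept) is held during sepsis, dehydration or acute decompensated heart failure.
- Give the DSMB a listing of randomised subjects whose screening creatinine was at or above the 1.33 limits. MDRD eGFR is computed from serum creatinine, so the values should be on file and no new test is needed.

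The cost is one amendment, plus a few otherwise eligible subjects lost if the alcohol or creatinine limits are added. Keeping eGFR 40 with a stated reason loses none on renal grounds.

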1.34 Privacy

As noted, we will advise participants to set their phone to password protected mode. Due to the nature of text messaging technology, there is a small potential privacy risk

when communicating through text messages. Text message communications are not encrypted and therefore this information can be read if intercepted while in transit. Although we have a strict confidentiality policy and the technology system we use to deliver text messages meets or exceed HIPAA standards, there is a possibility for the text messaging communications to be intercepted or accessed without the participant's authorization. Once delivered to the participant's mobile device, text messages are under his or her control and are his or her responsibility. By agreeing to participate in this study, participants accept this technology risk and release the research team, Vanderbilt, and Johns Hopkins from any liability arising from the use of text message communications in this program.

1.35 Financial Risk

Participants will only pay for text messages according to their mobile phone service plan. The intent of this study is to test the real world feasibility of this intervention in a PAH population across a range of disease severity. Therefore, there will be no early stopping rules. As stated in the consent form and reviewed at the time of enrollment, subjects may end participation at any time without prejudice.

Quality Control

Design strategies and monitoring activities throughout the study will ensure the integrity and high quality of the data. Design strategies include randomization of treatment assignment and training and certification of personnel. The rigorous monitoring program includes data queries and performance monitoring over the time of the trial.

1.36 Personnel Training

Prior to randomization of the first subject in the study protocol, each site PI will ensure that staff has completed appropriate training and that all documentation including sIRB approval (and local IRB approvals, if required) is completed and available. The purpose of training is to ensure that study personnel are carrying out the protocol in a consistent way and are adhering to good clinical practice guidelines. Staff will have current Human Subjects Training Certification on file. Before enrollment begins, study coordinators and research assistants who will perform the outcome assessments will be trained in all procedures, including completion of case-report forms (CRFs).

1.37 Coordinating Center (CC)

The coordinating center (CC) will be Vanderbilt University Medical Center. The coordinating center will be the central site responsible for organizing and managing activities and logistics for all collaborative components of the study, including oversight, and coordination of the multi-site study design, evaluation of progress, and data storage. The coordinating center will develop standard operating procedures for how each site collects data, plans for project management, subject recruitment and retention, performance milestones, scientific conduct of the trial, and dissemination of results.

1.38 Data Quality

The site PI and study coordinator will constitute the first line of monitoring of the safety of the human participants. They will perform continuous monitoring of data quality and completion of CRFs. Surveillance for AEs will consist of questioning subjects about potential AEs at every study contact, having subjects report any adverse event to the study team, and having subjects undergo vital sign checks and physical exams during each study visit. The CC will create computer modules to identify discrepancies and incomplete data. These reports are tracked until each problem is resolved and corrected in the database.

Periodic audits of each enrollment site will be conducted by the lead site. The monitoring staff will review database forms and source documents to ensure that the information on the forms is complete and consistent with the source documents. All consent forms will be audited. All study personnel are required to read the consent form and protocol.

Project team members at Vanderbilt listed as Key Study Personnel with existing electronic health record (EHR) system access rights will make use of REDCap Clinical Data Pull (CDP) tools. These tools are designed to enable transfer of relevant study-related data from the Vanderbilt Research Derivative and/or directly from the EHR into REDCap.

Data and Safety Monitoring and Reporting

1.39 Consent

Written consent will be obtained for enrollment from participants. For each consent process, study personnel will discuss the details of the study, the risks and benefits, and the subject's rights and responsibilities if they choose to participate in the trial and their right to refuse to participate. It will be made clear that their clinical care will not be affected by their decision. Subjects will be permitted to provide verbal consent over the phone prior to being scheduled for a screening visit. Documentation of verbal consent will be noted. Written consent will be obtained at the screening visit or before.

1.40 Institutional Review Board process

The CC and Field Centers will rely on a single IRB (sIRB) of record (Vanderbilt University Medical Center's IRB) and obtain approval and reliance agreements. When sIRB approval is obtained, site specific ICFs will be sent to the CC along with the notice of approval. These materials must be on file in the CC before a center can begin enrolling participants into the clinical trial.

1.41 Designated Medical Director

[name] will serve as the medical director for this trial. [name] serves as an attending physician in the Vanderbilt Medical Intensive Care Unit, the inpatient consult service, and the pulmonary hypertension service. [name] has outpatient clinics where she sees a variety of general pulmonary diseases and pulmonary vascular disease. She will be invited to attend weekly meetings with the PI and study personnel. She will be

available to discuss adverse events with the PI and respond to safety concerns from subjects or study personnel.

1.42 Monitoring

During phone calls and study visits, study personnel will review a checklist of signs or symptoms to detect any evidence of over-exertion or disease progression. Subjects will also be given a list of symptoms with definitions in lay language that may be related to overexertion and will be instructed to contact study personnel if symptoms arise. The list will include questions about excessive breathlessness with exertion, dizziness, presyncope/syncope, excessive fatigue, muscle soreness, increased use of as needed diuretics, orthopnea, and paroxysmal nocturnal dyspnea. Any positive responses will be reviewed with the medical director who will discuss these concerns with the subject to determine whether the symptoms are related to the intervention. If symptoms are likely attributable to the intervention, we will record it as an adverse event and decrease the step count goal to a tolerable level, depending on the severity of the symptoms and the judgement of the medical director. All serious adverse events will be reported to the DSMB, Vanderbilt Institutional Review Board, and NIH as described in Section 10.5.4.

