- Capacity of metabolomics profiles and clinical features at screening to predict response to the mHealth intervention or no intervention and/or metformin or placebo groups at week 12.

- Capacity of change in metabolomics profile and clinical features from screening to predict response to the mHealth intervention or no intervention and/or metformin or placebo groups at week 12.
- Difference in safety and tolerability between mHealth intervention or no intervention and/or metformin or placebo groups in PAH subjects over 12 weeks.
- Difference in fidelity of data collection and text transmission of the mHealth intervention over 12 weeks.
- Difference in patient satisfaction between mHealth intervention or no intervention and/or metformin or placebo groups at week 12.
- Difference in dropout rates between mHealth intervention or no intervention and/or metformin or placebo groups over 12 weeks.
- Difference in PAH-related hospitalizations between mHealth intervention or no intervention and/or metformin or placebo groups over 12 weeks.
- Difference in medication regimen escalation/reduction between mHealth intervention or no intervention and/or metformin or placebo groups over 12 weeks.
- Difference in incidence of death between mHealth intervention or no intervention and/or metformin or placebo groups over 12 weeks.

STUDY OBSERVATIONS:

- Subjects will be evaluated in person at screening (-2 weeks) and 12 weeks.
- Subjects will have telephone follow-up at weeks 1, 3, 6, and 9.
- HOMA-IR, estradiol and estrogen metabolites, lipid profiles, free fatty acids, acylcarnitine profiles, BNP levels, and other biomarkers will be assessed at screening and 12 weeks.
- Subjects will have six minute walk testing at screening and 12 weeks.
- Subjects will have a transthoracic echocardiogram at screening and 12 weeks.

- Subjects will answer quality of life questionnaires at screening and 12 weeks.
- Subjects at Vanderbilt will have cardiac and skeletal muscle MR spectroscopy screening and 12 weeks.
- Subjects at Vanderbilt will have muscle strength and function testing at screening and 12 weeks.

SAMPLE SIZE AND POWER:

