1.44 Definitions

1.44.1 *Unanticipated Problem (UP)*

Any incident, experience, or outcome that meets **all** of the following criteria:

- i. unexpected (in terms of nature, severity, or frequency) given a) the research procedures that are described in the protocol-related documents, such as the IRB-approved research protocol and informed consent document; and b) the characteristics of the subject population being studied;
- ii. related or possibly related to participation in the research (*Possibly related to participation in the research means there is a reasonable possibility that the AE, experience, or outcome may have been caused by the procedures involved in the research*); and
- iii. suggests that the research places subjects or others at a greater risk of harm (including physical, psychological, economic, or social harm) than was previously known or recognized.

1.44.2 *Adverse Event (AE)*

Any symptom, sign, illness or experience that develops or worsens in severity during the course of the study. Intercurrent illnesses or injuries should be regarded as AEs. Abnormal results of diagnostic procedures are considered to be AEs if the abnormality:

- i. results in study withdrawal
- ii. is associated with a serious AE
- iii. is associated with clinical signs or symptoms
- iv. leads to additional treatment or to further diagnostic tests
- v. is considered by the investigator to be of clinical significance

1.44.3 *Serious Adverse Event (SAE)*

Adverse reactions are classified as serious or non-serious. A *serious adverse event* is any AE that is:

- i. fatal
- ii. life-threatening
- iii. requires or prolongs hospital stay
- iv. results in persistent or significant disability or incapacity
- v. a congenital anomaly or birth defect
- vi. an important medical event

Important medical events are those that may not be immediately life threatening, but are clearly of major clinical significance. They may jeopardize the subject, and may require intervention to prevent one of the other serious outcomes noted above. For example, drug overdose or abuse, a seizure that did not result in in-subject hospitalization or intensive treatment of bronchospasm in an emergency department would typically be considered serious. All AEs that do not meet any of the criteria for serious should be regarded as **non-serious AEs**.

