1.45.2 Expectedness

AEs must be assessed as to whether they were expected to occur or were unexpected, meaning not anticipated based on current knowledge found in the protocol, investigator brochure, product insert, or label.

Expected: an AE known to be associated with the intervention or condition under study.

OHRP defines an **unexpected AE** as any AE occurring in one or more subjects participating in a research protocol, the nature, severity, or frequency of which is **not** consistent with either:

- i. the known or foreseeable risk of AEs associated with the procedures involved in the research that are described in a) the protocol-related documents, such as the IRB-approved research protocol, any applicable investigator brochure, and the current IRB-approved informed consent document, and b) other relevant sources of information, such as product labeling and package inserts; or
- ii. the expected natural progression of any underlying disease, disorder, or condition of the subject(s) experiencing the AE and the subject's predisposing risk factor profile for the AE.

1.45.3 *Relatedness*

- i. **Definite:** the AE is clearly related to the research procedures
- ii. **Probably:** the AE is likely related to the research procedures
- iii. **Possible:** the AE may be related to the research procedures
- iv. **Unlikely:** the AE is doubtfully related to the research procedures
- v. **Unrelated:** the AE is clearly not related to the research procedures

Possibly related to participation in the research: There is a reasonable possibility that the adverse event, experience, or outcome may have been caused by the procedures involved in the research.

For each identified AE, an AE entry on the appropriate form will be completed using the above classifications as soon as possible, updating as necessary. Reporting procedures should be started immediately (within 24 hours) upon learning of a SAE or UP.

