1.46 Interpretation of Definitions

1.46.1 *AE and UP Reporting Period*

The study period during which AEs must be reported is normally defined as the period from the initiation of any study procedures to the end of the study treatment follow-up. For this study, the study treatment follow-up is defined as 21 days following the last administration of study treatment (week 15 phone call).

1.46.2 *Preexisting Condition*

A preexisting condition is one that is present at the start of the study. A preexisting condition should be recorded as an AE if the frequency, intensity, or the character of the condition worsens during the study period.

1.46.3 *General Physical Examination Findings*

At screening, any clinically significant abnormality should be recorded as a preexisting condition. At the end of the study, any new clinically significant findings/abnormalities that meet the definition of an AE must also be recorded and documented as an AE.

1.46.4 *Post-study AE*

All unresolved SAEs or AEs that are possibly, probably, or definitely related to the study or study drug should be followed by the investigator until the events are resolved, the

subject is lost to follow-up, or the AE is otherwise explained. At the last scheduled visit, the investigator should instruct each subject to report any subsequent event(s) that the subject, or the subject's personal physician, believes might reasonably be related to participation in this study.

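### Section 1.42 ties adverse-event recording of checklist symptoms to attribution, against the protocol's own cause-neutral AE definition; followed literally, it could distort the between-arm safety comparison

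*Combined protocol and SAP*

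**What the plan says.** Section 1.42 (Monitoring) describes what happens at phone calls and visits: "study personnel will review a checklist of signs or symptoms to detect any evidence of over-exertion or disease progression". The items are breathlessness on exertion, dizziness, presyncope or syncope, fatigue, muscle soreness, greater use of as-needed diuretics, orthopnea and paroxysmal nocturnal dyspnea. Then: "Any positive responses will be reviewed with the medical director who will discuss these concerns with the subject". The purpose of that discussion is to decide whether the symptom is related to the intervention. The rule that follows is: "If symptoms are likely attributable to the intervention, we will record it as an adverse event". The same sentence provides for lowering the step goal. No action is given for a symptom judged not attributable.

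Other sections treat cause differently:

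- Section 1.44.2 defines an AE as "Any symptom, sign, illness or experience that develops or worsens in severity during the course of the study".
- Section 1.45.3 grades the relatedness of AEs in five levels. The lowest, Unrelated, reads: "the AE is clearly not related to the research procedures". It also requires: "For each identified AE, an AE entry on the appropriate form will be completed using the above classifications as soon as possible".
- Section 1.46.2 says: "A preexisting condition should be recorded as an AE if the frequency, intensity, or the character of the condition worsens during the study period".

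The secondary endpoints in the Protocol Summary include: "Difference in safety and tolerability between mHealth intervention or no intervention and/or metformin or placebo groups in PAH subjects over 12 weeks".

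**The concern.** Under 1.42, attribution comes before recording. Under 1.44.2 and 1.45.3, recording comes first and relatedness is a grade given to an event already on the form. For a checklist symptom that the medical director puts down to PAH, the two procedures point in different directions: 1.44.2 makes it an AE, and 1.42 gives no instruction to record it.

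This matters for the safety endpoint because attribution need not work the same way in each arm. Section 1.15 sets a step target for the intervention group and describes none for usual care, and the response in 1.42 is to lower a step goal. The attribution question is therefore framed around mHealth. Section 1.23 calls the trial single-blinded, a drafting note left in 1.25 says that two named people know the assignments, and the medical director's blinding is not stated. The same breathlessness could be entered as an AE in an mHealth subject and not in a usual-care subject. The checklist is also meant to pick up disease progression, which a clinician would readily attribute to PAH rather than to the intervention.

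**Working it through.** **Step 1: side by side.** Take a checklist symptom that is new or worse during the study.

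| Medical director's view | Section 1.42 | Sections 1.44.2, 1.45.3, 1.46.2 |
|---|---|---|
| Likely attributable | Record as AE | Record as AE, then grade relatedness |
| Not likely attributable | No instruction | Record as AE, then grade relatedness (including Unlikely or Unrelated) |

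The conflict is confined to the second row. If every new symptom were to be entered anyway, the condition in 1.42 would have no effect on recording, so exclusion is a natural reading, though not an explicit rule.

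**Step 2: what the documents allow to be computed.** They give no expected symptom rate, attribution rate or power for safety, so there is no figure to reproduce. The calculations below illustrate the mechanism only, and every rate in them is assumed.

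Let s be the true proportion with a new or worse symptom and a the probability that it is judged attributable. If 1.42 is followed literally, the recorded proportion is r = s × a. The groups are 35 per arm (the completers planned in 1.26) or 70 per side (two arms pooled, 2 × 35). The test is a two-sided 0.05 Pearson chi-square without continuity correction, with its rejection probability summed exactly over two binomials.

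**Step 3: no true difference, s = 0.30 on both sides.**

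| a, mHealth v usual care | r = s × a | Rejection, 35 v 35 | Rejection, 70 v 70 |
|---|---|---|---|
| 0.50 v 0.50 | 15% v 15% | 5.3% | 4.9% |
| 0.50 v 0.20 | 15% v 6% | 24.9% | 42.0% |
| 0.60 v 0.10 | 18% v 3% | 60.3% | 87.7% |

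Equal attribution leaves the false-positive rate near 5%. Unequal attribution raises it.

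**Step 4: a true difference with equal attribution.** Let s be 0.40 v 0.20 and a = 0.50 on both sides. The recorded proportions are 0.40 × 0.50 = 20% and 0.20 × 0.50 = 10%, so the difference falls from 20 to 10 points. Power falls from about 45% to 22% with 35 per arm, and from about 75% to 38% with 70 per side.

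**Step 5: sensitivity to the control-side assumption.** Use all 160 planned subjects, 80 per side, with s = 0.30 (24 each) and half of the mHealth symptoms attributed (12 recorded). Two-sided Fisher tests give:

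| Recorded AEs | p |
|---|---|
| 12/80 v 0/80 | 0.0003 |
| 12/80 v 3/80 | 0.027 |
| 12/80 v 4/80 | 0.06 |
| 12/80 v 5/80 | 0.12 |

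The apparent excess depends heavily on how many usual-care symptoms are attributed. Zero is the extreme case.

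**Step 6: after rewording.** If recording no longer depends on attribution, a = 1 for entry in every arm and r = s. Sample size and primary-endpoint power do not involve r and do not change.

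**The case against.** A reader might infer that unattributed symptoms are recorded only when attributed, that they go uncounted, and that the safety comparison is therefore biased. The documents do not support that reading.

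- The text says if, not only if. It is silent on the other case and does not forbid recording.
- Other procedures have no causality filter. Section 1.38 asks about potential AEs at every contact, 1.19.3 has symptoms reviewed and recorded at each call, Table 2 has separate rows for symptom assessment and adverse events, 1.45.3 requires an entry for each identified AE, and 1.46.6 asks that all routine AEs be reported to the coordinating center. Section 1.46.2 directly covers worsening PAH.
- Serious events are reported under 1.42 itself, all hospitalizations under 1.22.16, and PAH drug additions and dose changes under 1.22.15, whatever the cause. A hidden excess of serious right-heart worsening is therefore not a fair inference.
- Attribution in usual care need not be zero. By design, half of those subjects take metformin and half matching placebo, and 1.33 lists dizziness, dyspnea and myalgia among metformin reactions, which overlap the checklist. If the intervention includes study drug, some of their symptoms will be attributed.

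All of this stands, and it narrows the point. It does not remove it: staff have one specific instruction that makes recording conditional and several general ones that do not. A symptom noted in a call log is not an AE entry with severity and relatedness, so it does not by itself restore the comparison.

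**Conclusion.** Section 1.42 is inconsistent with 1.44.2, 1.45.3 and 1.46.2, and the passages must be reconciled. That conclusion rests on the text alone.

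The effect on the safety comparison is conditional. It arises only if sites follow 1.42 in preference to the AE definition. Bias then requires attribution to differ by arm, which is plausible because only mHealth subjects have a step goal but is not shown. If attribution is equal, the consequence is dilution of a real difference. Direction and size cannot be stated from the documents; the figures above show how the mechanism works and are not estimates for this trial.

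The exposure is mainly non-serious events without hospitalization. This is a consistency correction affecting a secondary safety endpoint. It does not touch the primary endpoint, sample size or power.

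**What to change.** Reword the sentence in 1.42 so that every checklist symptom that is new, or worse than at screening, is recorded as an AE under 1.44.2 in all four arms. Have the medical director's attribution entered separately on the 1.45.3 scale. State that the between-arm safety comparison uses all-cause AEs. Leave the existing step-goal provision as it is.

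The cost is a short protocol amendment and somewhat more AE form entry. The symptoms are already asked about at calls and visits, so no new assessment is needed.
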